2.4.4.4 Additional efficacy analysis(es)

The tertiary/exploratory variables (see Section 2.1.3.3) will be summarized by treatment group, using descriptive statistics for continuous variables for ITT population, except for PROs.

A plot with the mean glucose profile over 24-hour period will be presented. For each patient, the data will be summarized for each 1-hour interval over 24-hour period, eg, [00:00, 01:00), [01:00, 2:00), ..., [23:00, 24:00) taking the average of CGM readings from usable CGM days. Then, the mean profile will be calculated taking the average across all patients at each interval and plotted at the midpoint of each 1-hour interval.

For PRO, the analyses are described in Section 2.4.7.

Change from baseline in 7-point SMPG profiles (pre-prandial and 2-hour postprandial plasma glucose at breakfast, lunch and dinner, and at bedtime) to Week 12 will be described by treatment group using mean and SD.

A figure representing the mean (+/- SE) at baseline and Week 12 per time point as well as change from baseline at Week 12 will be produced by treatment group.

2.4.5 Analyses of safety data

The summary of safety results will be presented by treatment group classifying each patient in the group corresponding to the actual treatment received.

General common rules

All safety analyses will be performed on the safety population by actual treatment received as defined in Section 2.3.2, unless otherwise specified, using the following common rules:

- Safety data in patients who do not belong to the safety population (eg, exposed but not randomized) will be listed separately,
- The baseline value is defined as the last available value before the first injection of open-label IMP,
- The analysis of the safety variables will be essentially descriptive.

2.4.5.1 Analyses of hypoglycemia events

Incidence of patients with at least one hypoglycemia event

A frequency table showing the number and % of patients experiencing at least one hypoglycemic event will be presented for any hypoglycemia and for each type of hypoglycemia (see

Section 2.1.4.6), overall and according to time of occurrence (nocturnal [ie, 00:00 to 05:59], for any time of day and daytime [ie, 06:00 to 23:59] during the on-treatment period.

The Odds Ratio and its corresponding 95% CI for the Toujeo arm over the Tresiba arm for each hypoglycemic event (nocturnal and any time of the day) during the on treatment period will be estimated by a logistic regression model adjusted on randomization strata of screening HbA1c.

Number and rate of hypoglycemia event

The number and rate of hypoglycemic events (in patient-year of exposure) will be determined for any hypoglycemia and for each type of hypoglycemic event, overall and according to time of occurrence (nocturnal [ie, 00:00 to 05:59], any time of the day) during the on treatment period and in the pre-treatment period.

For each type of hypoglycemic event during the on treatment period, the rate ratio, and its corresponding 95% CI, for the Toujeo arm over the Tresiba arm will be estimated using an over-dispersed Poisson regression model adjusted on randomization strata of screening HbA1c.

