Visit ^a	1	2	3	4	5	6	7 2	8	9	10	11 2	12 2	13 2	14	15	16 2	17 2	18 ^b		19 ^d	
Day	-42/-35	-28	-20	-14	-7	1	7	14	21	28	35	42	48	56	64	71	78	84		86-88	
Collect CGM device and upload CGM data						Х												х	х		Upload CGM data to the site computer with QuintilesIMS Study Management Suite Software
Training: Glucometer, SMPG profiles, study diary		Х																			
Glucometer dispensation		Х																			
Fasting SMPG ^g		Х	Х	Х	Х	Х	Х	Х	Х	Х	Х	Х	Х	Х	Х	Х	Х	Х	Х	Х	Values of last 3 measurements before each visit must be recorded in eCRF
2hPPG							Х	Х	Х	Х	Х	Х	Х	Х	Х	Х	Х				Regularly as instructed by investigator
7-point SMPG						Х												Х	Х		
SMPG data upload to site's PC						Х								Х	Х			Х	Х	Х	Server independent from eCRF
Re-training: Glucometer, SMPG profiles, study diary		Х	Х			Х								Х	Х			Х			

	Screening (weeks)	I	Run-in	(week	s)		Intervention period (weeks)					Follow up	Notes								
Procedure	-6/-5	-4	-3	-2	-1		1	2	3	4	5	6	7	8	9	10	11	12	EOT ^C	2 to 4 days after last IMP dose	Visit Windows: Site visits: ±3 days Phone call visits: ±1 day relative to Visit 6
Visit ^a	1	2	3	4	5 2	6	7 2	8	9	10 2	11	12 2	13 2	14	15	16	17 2	18 ^b		19 ^d	
Day	-42/-35	-28	-20	-14	-7	1	7	14	21	28	35	42	48	56	64	71	78	84		86-88	
HbA1c, FPG	Х					х												Xh	х		Central lab h:In case of premature EOT, : HbA1c, FPG to be measured at Week 12
C-peptide	Х																				Central lab
Hematology, clinical chemistry	Х																				See Appendix 2, Section 10.2
Pregnancy test (WOCBP only)	Х					х												х			Serum pregnancy test for screening; urine pregnancy test for subsequent monitoring (if positive to be confirmed by a serum test).
AE/SAE	AE To be assessed and reported if any throughout the study																				
Hypoglycemia recording		To be assessed and reported if any throughout the study																			
DTSQs						Х												Х			
DTSQc																		Х			
MOS-sleep						Х												Х			

	Screening (weeks)	Run-in (weeks)								Ir	nterve	entio	n per	iod (v	veeks)				Follow up	Notes
Procedure	-6/-5	-4	-3	-2	-1		1	2	3	4	5	6	7	8	9	10	11	12	EOT ^C	2 to 4 days after last IMP dose	Visit Windows: Site visits: ±3 days Phone call visits: ±1 day relative to Visit 6
Visit ^a	1	2	3	4 2	5 2	6	7	8	9	10 2	11 2	12 2	13 2	14	15	16 2	17 2	18 ^b		19 ^d	
Day	-42/-35	-28	-20	-14	-7	1	7	14	21	28	35	42	48	56	64	71	78	84		86-88	
WPAI						Х												Х			

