- a Telephone calls to monitor insulin titration should be scheduled by the Investigator for Weekly in between of site visits for all patients, unless the patient is attending the study site for sensor replacement. Option to come to site on D-10 and D74 for sensor replacement.
- b Visit 18 will occur at Week 12 regardless of the treatment end date, and procedures ticked below should be done
- c EOT (End Of Treatment) visit will occur in case of premature discontinuation of study treatment before Visit 18 at week 12 and related procedures ticked below should be applied. If at the time of such premature discontinuation there is ongoing CGM recording, it should be completed, and EoT vist done thereafter. Afterward, the patients should continue in the study up to the scheduled date of study completion. See Section 7.1
- d If EOT visit occurs beyond 2 to 4 days after last administration of study drug then Visit 8 will not be required. EOT and safety follow up can be done at the same time, if occurs within 2 to 4 days after last IMP dose.
- e The Investigator should contact IRT either at Visit 18 or at EOT visit in case of premature end of treatment (whichever occurs first), to register end of treatment.
- f For each 20 day CGM period to be fully evaluable for CGM it is necessary to obtain a minimum of 10 days (not necessarily consecutive) of useable CGM data. Useable CGM data for a day/a 24-hour CGM profile are defined as: at least 80% time of records per 24 hours; no gap (missing data) lasting for ≥2 hours per 24 hours besides the warm-up time for the sensor after insertion.
- g SMPG to be performed by the patients from run-in period and throughout the study duration:
 - 1. Fasting (pre-breakfast/pre-injection) SMPG: daily until dose stabilization of basal insulin has been completed and fasting SMPG goal is reached. Thereafter, the number of fasting SMPG checks can be reduced according to the Investigator's judgment, however at least 3 fasting (pre-breakfast) SMPG measurements per week should be done.
 - 2. SMPG values throughout the study, starting after Visit 2. Patients should test their SMPG following the Investigator's instructions for mealtime insulin titration.
 - 3. 2hPPG (post prandial plasma glucose); regularly as instructed by investigator to guide meal time insulin titration;

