1.4 STUDY PLAN

The study consists of a 1- or 2-week screening period, followed by a 4-week run-in period, and a 12-week randomized treatment period.

During the first 2 weeks of the run-in period (Weeks -4 and -3), patients will undergo treatment stabilization of their current basal and mealtime insulin treatment and will be trained and tested on how to perform study-related procedures. During the (-3) - (-1) weeks of run-in, patients will wear a CGM device, blinded to both patients and Investigators. During these 20 consecutive days, CGM readings will be collected as CGM assessment at baseline.

During the randomized treatment period, CGM readings will also be collected in the same fashion as in the run-in period during Weeks 10-12. This will be the CGM assessment at Week 12.

During the entire study starting after the screening period, patients will perform Self-Monitoring of Plasma Glucose (SMPG) as specified in the study flow chart. The SMPG readings will be used to guide insulin dose titration for optimal glycemic control.

Figure 1 - Graphical study design

At the end of the study, the patients will be followed-up for between 2 to 4 days after the last Investigational Medicinal Product (IMP) dose to collect post-treatment safety information.

Figure 1 is a representation of the study schema.

Abbreviations: CGM = continuous glucose monitoring, HbA1c = glycated hemoglobin, , MDI = multiple daily injection, R = randomized, SMPG = self-monitoring of plasma glucose, T1 diabetes = type 1 diabetes

The schedule of activities (SOA) for the study is presented in Section 1.3 of the protocol.

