2.1.4 Safety endpoints

To address the secondary objective of evaluating the safety of insulin glargine 300 IU/mL in comparison to insulin degludec 100 IU/mL, the following endpoints will be observed

- Number of patients with adverse events (see Section 8.3 of the protocol).
- Number of patients with at least one hypoglycemic event from baseline to Week 12.
- Number of hypoglycemic events per participant-year from baseline to Week 12.

The safety analysis will be based on the reported adverse events (AEs) and other safety information, such as vital signs. The specific safety parameter of interest for insulin treatment is hypoglycemia.

Observation period

For all safety data, the observation period will be divided as follows:

- The pre-treatment phase is defined as the time from when the patients sign the informed consent to first injection of IMP (excluded).
- The on-treatment phase is defined as the time from the first injection of IMP (included) up to 2 days after the last injection of IMP.
- The post-treatment phase is defined as the time after the on-treatment phase until the end of the study (Follow up Visit).

On-study observation period is defined as the time from start of treatment until the end of the study (defined as last protocol planned visit or the resolution/stabilization of all serious adverse events (SAEs) and AEs of specific interest (AESI) as defined in the protocol).

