2.1.4.6 Hypoglycemia events

Hypoglycemia events will be evaluated during pre-treatment and on-treatment period (see Section 2.1.4).

All reported hypoglycemia events will be classified according to American Diabetes Association (ADA) classification as follows:

- Severe hypoglycemia: an event that 'Required Assistance Because Subject Was Not Capable of Helping Self'.
- **Documented symptomatic hypoglycemia**: an event during which typical symptoms are accompanied by a measured plasma glucose concentration less than 3.9 mmol/L (<70 mg/dL).
- Asymptomatic hypoglycemia: an event with no symptoms of hypoglycemia but a documented measured plasma glucose concentration less than 3.9 mmol/L (<70 mg/dL).

In addition, the following events will be also considered:

- Documented symptomatic hypoglycemia with measured plasma glucose concentration less than 3.0 mmol/L (<54 mg/dL).
- Asymptomatic hypoglycemia with measured plasma glucose concentration less than 3.0 mmol/L (<54 mg/dL).

- Hypoglycemia (symptomatic or asymptomatic) documented by a measured plasma glucose concentration less than 3.9 mmol/L (<70 mg/dL).
- Hypoglycemia (symptomatic or asymptomatic) documented by a measured plasma glucose concentration of <3.9 mmol/L (< 70 mg/dL) and \geq 3.0 mmol/L (\geq 54 mg/dL).
- Hypoglycemia (symptomatic or asymptomatic) documented by a measured plasma glucose concentration less than 3.0 mmol/L (<54 mg/dL).
- Severe and/or symptomatic hypoglycemia documented by plasma glucose concentration less than 3.9 mmol/L (<70 mg/dL).
- Severe and/or symptomatic hypoglycemia documented by plasma glucose concentration less than 3.0 mmol/L (<54 mg/dL).

In addition to anytime of the day (00:00 to 23:59), hypoglycemia events will be evaluated at the following time periods:

- Nocturnal hypoglycemia: any hypoglycemic event that occurs between 00:00 and 05:59.
- Diurnal hypoglycemia: any hypoglycemic event that occurs between 06:00 and 23:59.

Note: CGM values will not be considered for identifying hypoglycemia.

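### The hypoglycemia rate-ratio model leaves out each patient's run-in hypoglycemia, which is already recorded; the loss is precision only, and only for frequent event categories

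*SAP*

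**What the plan says.** For each type of event, SAP 2.4.5.1 estimates the Toujeo to Tresiba rate ratio, with a 95% CI, from an "over-dispersed Poisson regression model adjusted on randomization strata of screening HbA1c". Appendix A repeats the model. No other covariate is named, and no exposure offset is stated, although the rates are expressed per patient-year.

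The run-in information exists. The Protocol's Schedule of Activities (1.3) says of hypoglycemia recording: "To be assessed and reported if any throughout the study". It also requires "SMPG to be performed by the patients from run-in period and throughout the study duration", with the sponsor's glucometer dispensed at Visit 2. SAP 1.4 describes a screening period "followed by a 4-week run-in period, and a 12-week randomized treatment period". SAP 2.1.4.6 states: "Hypoglycemia events will be evaluated during pre-treatment and on-treatment period". SAP 2.4.5.1 then tabulates the number and rate of events "during the on treatment period and in the pre-treatment period".

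On status, SAP 2.1.4 says "The specific safety parameter of interest for insulin treatment is hypoglycemia", and SAP 2.4.5 says "The analysis of the safety variables will be essentially descriptive".

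**The concern.** Patients with type 1 diabetes differ widely in how often they have hypoglycemia, and a patient's own recent rate is the natural baseline value of this endpoint. The SAP follows that logic elsewhere. The primary and secondary CGM endpoints, HbA1c, FPG and the questionnaire change scores are each adjusted for their own baseline, and DTSQc is adjusted for baseline DTSQs (SAP 2.4.4 and 2.4.7). The hypoglycemia rate ratio is adjusted only for a two-level HbA1c stratum.

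Between-patient variation that the run-in count could explain therefore stays in the error and widens the interval. Neither document contains a power calculation for hypoglycemia, so the interval is what readers will use to judge whether the insulins differ.

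**Working it through.** **The plan's own figure.** There is none for this comparison. The only sample-size calculation is for time in range: (1.96 + 1.282)² × 1.81 × 14.7² / 5.6² = 131.09 per group, stated as 131, with 169 per group randomized. The 169 is used below.

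**Inputs from the documents.** 169 per arm; 28-day run-in; 84-day treatment; over-dispersed Poisson model with treatment and HbA1c stratum.

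**Assumed inputs.** The event rate; the squared CV of patients' true rates, k; and the correlation ρ between a patient's run-in and on-treatment log rates.

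**Step 1: what a baseline covariate could remove.** With equal exposure and mean on-treatment count μ, Var(log RR) ≈ (2/n)(1/μ + k). Only the k part can be explained by a patient's history. At 40 events per patient-year, μ = 40 × 84/365.25 = 9.20. With k = 1, SE = √[(2/169)(0.109 + 1)] = 0.115, and the k share is 1/1.109 = 90%. The mean run-in count is 40 × 28/365.25 = 3.07.

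**Step 2: what the run-in count does remove.** Trials were simulated with log-normal patient rates, and the planned model was compared with the same model plus log(run-in count + 0.5). The gain is the fall in the empirical SE, meaning the actual spread of the estimates across simulated trials. Results for k = 1 (CV 1), from separate runs of 1,500 to 2,000 trials per setting:

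| Events per patient-year | Mean run-in count | μ | SE from formula | k share | SE fall, ρ = 0.5 | SE fall, ρ = 0.8 |
|---|---|---|---|---|---|---|
| 2 | 0.15 | 0.46 | 0.194 | 32% | 0% | 1% |
| 10 | 0.77 | 2.30 | 0.130 | 70% | 1-3% | 6-8% |
| 30 | 2.30 | 6.90 | 0.116 | 87% | 5% | 17-18% |
| 40 | 3.07 | 9.20 | 0.115 | 90% | 5% | 17-19% |

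The simulated unadjusted SEs agree with the formula: 0.112-0.116 at 40 and 0.131-0.133 at 10. At 2 they are slightly higher (0.202-0.203), because the simulation also included a stratum effect that lowered the mean rate. The spread within a cell is between-run variation. For infrequent events most run-in counts are zero, so the covariate carries almost nothing.

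Example at 40 per patient-year and ρ = 0.8: the SE falls from 0.112 to 0.093. The 95% limits around a ratio of 1 move from a factor of 1.24 either way to 1.20.

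For k from 0.5 to 2 and ρ from 0.5 to 0.8, the SE fall is 5-23% at 40, 1-13% at 10 and 0-3% at 2. At ρ = 0 there was no gain.

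**Step 3: is the adjusted interval honest?** Two-sided 5% type I error at 40 per patient-year and ρ = 0.8:

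| k | Planned model | Adjusted, Pearson scale | Adjusted, robust SE |
|---|---|---|---|
| 1 | 0.047 | 0.076 | 0.058 |
| 2 | 0.055 | 0.095 | 0.060 |

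The worst setting run (60 per patient-year, k = 2) reached 0.110 with the Pearson scale. Across that wider set of settings, robust errors gave 0.049-0.076.

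**The case against.** The strongest case against acting is that the rate ratio has no hypothesis, margin or place in the testing hierarchy (SAP 2.4.4.3), that the safety analysis is declared descriptive, and that Protocol Table 8 asks only for rates by group. No stated decision depends on the interval's width. This limits the importance of the point but does not remove it: the SAP still reports a between-arm ratio with a 95% CI, and it baseline-adjusts questionnaire scores that it also presents as descriptive.

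The correlation may also be low. Run-in is on the previous basal insulin, with stabilization in its first two weeks. Treatment then brings a new insulin, possibly a new injection time, and titration expected up to Week 8 (Protocol 4.1, 6.1 and 6.6.1.2). This stands, and it is why no single percentage can be claimed.

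A reader might go further than the documents allow in four ways:

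- **That the planned rate ratio is biased or invalid.** It is not. Treatment is randomized, the planned model's type I error was close to nominal, and under a log link the ratio is collapsible, so the covariate does not change its target.
- **That the gain is what the two fitted models' printed SEs show.** At 30 per patient-year and ρ = 0.7 the printed SE falls 17%, but the empirical SE falls 11-12%. At 60, with ρ up to 0.9, the figures are up to 38% and 30%. The difference is understated uncertainty.
- **That one extra covariate is enough, for every category.** Step 3 shows that the error structure must change too. At 0.2 events per patient-year there was no real gain and some fits were unstable.
- **That hypoglycemia is the only outcome without baseline adjustment.** Exploratory CGM endpoints are only summarized (SAP 2.4.4.4).

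**Conclusion.** The omission is real, and correcting it is worthwhile but modest. The plan collects and tabulates run-in hypoglycemia and then leaves it out of the rate-ratio model. The cost is precision alone, and it falls on frequent categories such as any hypoglycemia and events below 70 mg/dL.

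For CV 1 and a correlation of 0.5 to 0.8, the empirical SE would fall about 5-19% at 30-40 events per patient-year, 2-8% at 10, and 0-2% at 2-3. These figures depend on assumed rates, dispersion and correlation, because the documents supply none. A weaker correlation shrinks them towards zero.

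**What to change.** In SAP 2.4.5.1 and Appendix A, for the rate-ratio model only:

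1. For frequent categories, add log[(run-in count + 0.5)/run-in days] of the same category as a continuous covariate. Count from Visit 2 to before the first IMP dose. This is shorter than the SAP's pre-treatment phase, which starts at consent, before the sponsor's glucometer is dispensed.
2. Keep the HbA1c stratum, and state the log of on-treatment exposure as the offset.
3. Use robust (sandwich) standard errors in place of the Pearson scale factor alone.
4. Keep the planned model for severe and other rare categories, and fix the rule that separates frequent from rare without reference to treatment arm.
5. Record all of this before database lock. Added after results are seen, it would be open to challenge.

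Leave the logistic model as planned. An odds ratio is not collapsible, so the same covariate would change what it estimates.

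The cost is slightly more programming and a separate rule for rare categories. No new data, visits or patients are needed.

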2.4.5.2 Analyses of adverse events

Generalities

The primary focus of AE reporting will be on TEAEs. Pre-treatment and post-treatment AEs will be described separately.

If an adverse event date/time of onset (occurrence, worsening, or becoming serious) is incomplete, an imputation algorithm will be used to classify the adverse event as pre-treatment, treatment-emergent, or post-treatment. The algorithm for imputing date/time of onset will be conservative and will classify an adverse event as treatment emergent unless there is definitive information to determine if it is pre-treatment or post-treatment. Details on classification of adverse events with missing or partial onset dates are provided in Section 2.5.4.

Adverse event incidence tables will be presented by SOC, HLGT, HLT, and PT, sorted in alphabetical order for each treatment group, showing the number (n) and percentage (%) of patients experiencing an adverse event. Multiple occurrences of the same event in the same patient will be counted only once in the tables within a treatment phase. The denominator for computation of percentages is the safety population within each treatment group.

Sorting within tables ensures the same presentation for the set of all adverse events within the observation period (pre-treatment, treatment-emergent, and post-treatment). For that purpose, the table of all treatment-emergent adverse events presented by SOC and PT sorted by the internationally agreed SOC order and decreasing frequency of PTs within SOCs will define the presentation order for all other tables unless otherwise specified. Sorting will be based on results for the Toujeo treatment group.

A listing of SAEs and listing of withdrawals due to AEs will be presented.

Analysis of all treatment-emergent adverse events

The following treatment-emergent adverse event (TEAE) summaries will be generated for the safety population.

- Overview of TEAEs, summarizing the number (%) of patients with any
 - TEAE
 - Serious TEAE
 - TEAE leading to death
 - TEAE leading to permanent treatment discontinuation
 - TEAE related to IMP
- The number (%) of patients experiencing TEAE(s) presented by PT, sorted by decreasing incidence of PT in the Toujeo treatment arm.
- All TEAEs by primary SOC, HLGT, HLT, and PT, showing number (%) of patients with at least 1 treatment-emergent adverse event sorted by the SOC internationally agreed order. The other levels (HLGT, HLT, PT) will be presented in alphabetical order.
- All TEAEs by primary SOC and PT, showing the number (%) of patients with at least 1 treatment-emergent adverse event, sorted by the internationally agreed SOC order and by decreasing incidence of PTs in the Toujeo treatment arm within each SOC.
- All TEAEs related to IMP by primary SOC and PT, showing the number (%) of patients with at least 1 treatment-emergent adverse event, sorted by the internationally agreed SOC order and by decreasing incidence of PTs in the Toujeo treatment arm within each SOC.

Analysis of all treatment emergent serious adverse event(s)

- All treatment-emergent serious adverse events by primary SOC, HLGT, HLT, and PT, showing the number (%) of patients with at least 1 serious treatment-emergent adverse event, sorted by the internationally agreed SOC order. The other levels (HLGT, HLT, PT) will be presented in alphabetical order.
- All treatment-emergent serious adverse events by primary SOC and PT, showing the number (%) of patients with at least 1 serious treatment-emergent adverse event, sorted by the internationally agreed SOC order and by decreasing incidence of PTs in Toujeo treatment arm within each SOC.
- All treatment-emergent serious adverse events related to IMP, by primary SOC and PT, showing the number (%) of patients with at least 1 treatment-emergent serious adverse event, sorted by the internationally agreed SOC order and by decreasing incidence of PTs in Toujeo treatment arm within each SOC.
- All treatment-emergent serious adverse events leading to treatment discontinuation, by primary SOC and PT, showing the number (%) of patients sorted by the internationally agreed SOC order and by decreasing incidence of PTs in Toujeo treatment arm within each SOC.

Analysis of all treatment-emergent adverse event(s) leading to treatment discontinuation

• All treatment-emergent adverse events leading to treatment discontinuation, by primary SOC and PT, showing the number (%) of patients sorted by the internationally agreed SOC order and by decreasing incidence of PTs in the Toujeo treatment arm within each SOC.

Analysis of adverse events of special interest

• A listing of patients with symptomatic overdose with IMP/NIMP. Pregnancy will be listed separately.

Analysis of pre-treatment and post-treatment adverse events

An overview of pre-treatment and/or post-treatment adverse events will be presented as a listing if only a few, otherwise as a summary (presenting number of patients with any pre-/post-treatment adverse events, serious pre-/post-treatment adverse events, pre-/post-treatment adverse events leading to death).

- All pre-treatment adverse events by primary SOC and PT, showing the number (%) of patients with at least 1 pre-treatment adverse event, sorted by the internationally agreed SOC order and PT will be presented by alphabetical order.
- All post-treatment adverse events by primary SOC and PT, showing the number (%) of patients with at least 1 post-treatment adverse event, sorted by the internationally agreed SOC order and PT will be presented by alphabetical order.

In case of a low number of events (pre-treatment and post-treatment), a only listing will be provided.

